4.2.2 Calculation of percentages

Missing values will not be included in the denominator count when computing percentages.

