4.2.4 Handling of missing data

There is no imputation of missing values, unless specified otherwise. Frequency of missing values will be tabulated for categorical variables.

Handling of missing date (time) or partially known date (time) is described in Section [5.3](#) for time since TTP diagnosis and in Section [7.1.1](#) for adverse events.

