4.3.3 Handling of unscheduled assessments

Pre-dose unscheduled measurements: the latest non-missing pre-dose unscheduled measurement may be used for the possible imputation of a missing baseline (see Section 4.3.1). In all other cases, the value will only be listed.

Post-dose unscheduled measurements: the original scheduled measurement will be used for the analysis tables. Unscheduled samples will not be used in the descriptive statistics, but will be shown in listings.

Unscheduled measurements will be taken into account for derivation of time to event parameters and area under the curve (AUC). They will also be used if there is a worst-case determination over a period of time.

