4.3.6 Presentation of treatment groups

The following treatment group labels will be used in the tables, listings and figures, unless specified otherwise:

- Caplacizumab
- Placebo
- Open-label (OL) Caplacizumab

Treatment groups Caplacizumab and Placebo refer to the initial treatment group prior to a potential switch to open-label caplacizumab, and only data up to the switch are used in the analyses of these treatment groups. The OL Caplacizumab treatment group will only be used for analyses after the switch to open-label caplacizumab.

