- Proportion of subjects who have a platelet count $\geq 150 \times 10^9/L$ on Day 1, 2, 3, 4, 5 and Day 10 and end of study drug treatment (i.e., last weekly visit during the DB or OL treatment period) will be summarized by treatment group (Caplacizumab, Placebo, OL Caplacizumab).
- Proportion of subjects with refractory TTP, defined according to Scully et al. (2016) as lack of sustained platelet count increment or platelet counts $< 50 \times 10^9/L$ and persistently raised LDH ($> 1.5 \times$ ULN) despite 5 plasma exchanges and steroid treatment will be summarized by treatment group (Caplacizumab, Placebo). Refractory TTP is derived as follows: (platelet count at Day x $<$ platelet count at Day x-1 for at least 1 value of x with x=2,...,5) and (LDH $> 1.5 \times$ ULN from Day 1 to Day 5). Subjects who have reached platelet count response (primary endpoint) by Day 5 will be considered as not refractory to TTP. Missing values will be imputed by using multiple imputation (Markov Chain Monte Carlo) by

averaged simulated parameter values, except if the subject discontinued prior to Day 5. In that case, the subject will not be considered in the analysis.

- Time to stop of daily PE: A KM analysis will be conducted with time to stop of daily PE within the DB treatment period as dependent variable and treatment group (Caplacizumab, Placebo) as independent variable. Time to stop of daily PE is defined as: date of daily PE stop - date of first i.v. loading dose of study drug after randomization + 1 day.
- The number of PE days and the total PE volume (absolute and normalized) in the DB treatment daily PE period and the overall treatment period will be summarized by treatment group. For this analysis the treatment groups are defined as
 - Caplacizumab + OL Caplacizumab
 - Placebo + OL Caplacizumab

Subjects will thus be analyzed according to their initial treatment group, both before and after switch to open-label caplacizumab. The number of PE days is defined as the total number of days on which PE is documented. The absolute total PE volume is given by the sum over all PE days of the amount exchanged in liter, while the normalized total PE volume is calculated as the sum over all PE days of the multiple of plasma volume exchanged.

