Similar to primary endpoint without the requirement to stop daily PE within 5 days. Kaplan-Meier analysis stratified for GCS at randomization, including a two-sided stratified Log-rank test. The output will include number of events, number of censored values, median, 25% percentile and 75% percentile of time to event with 95% CIs and p-value of the log-rank test as well as the hazard ratio (including CI) of the corresponding Cox proportional hazards model (see table 14.2.1.1.10 below for more details on the Cox model).

The table will be presented both by GCS category, and overall, i.e. unadjusted by GCS category.

Population: ITT population.

Table 14.2.1.1.10: EFF: Platelet count – Sensitivity: Cox proportional hazards mode: Time to first platelet count $\geq 150 \times 10^9/L$ (ITT - dPE stop within 5 days not required)

Similar to primary endpoint without the requirement to stop daily PE within 5 days.

Cox proportional hazards regression model with time to platelet count response as dependent variable and treatment group and GCS category as independent variables. Table consists of 2 parts:

Part 1: Results of the Cox proportional hazards model including hazard ratio and CI on hazard ratio.

Part 2: Assumption testing including supremum test on proportion of simulated score processes that yielded a maximum score larger than the maximum observed score and a graphical representation of observed score processes per covariate

Part 3 (conditional): Results of the expanded Cox proportional hazards model including odds hazard ratio and CI on hazard ratio. This part will only be reported when the original assumption of proportional hazards does not hold and time interaction(s) need to be added.

Population: ITT population.

Table 14.2.1.1.11: EFF: Platelet count – Proportion of subjects with platelet count $\geq 150 \times 10^9/L$

CONFIDENTIAL

Frequency tabulation of having a platelet count $\geq 150 \times 10^9/L$. The following time points will be shown: Day 1, Day 2, Day 3, Day 4, Day 5, Day 10 and end of study drug treatment (i.e., last weekly visit during the DB or OL treatment period).

Population: ITT population.

Table 14.2.1.1.12: EFF: Platelet count – AUC until Day 5

Descriptive statistics of AUC of platelet count until Day 5.

Population: ITT population.

Table 14.2.1.1.13: EFF: Platelet count – Actual values at each time point

Descriptive statistics of platelet count at each time point including (5% 10% 25% 75% 90% and 95% percentiles).

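### The Day 10 row for platelets ≥150 × 10⁹/L is labelled ITT but is computed on a subset selected by platelet response

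*SAP*

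**What the plan says.** SAP 6.2.2 summarises, by treatment group and on the ITT population, the proportion of subjects with a platelet count of at least 150 × 10⁹/L "on Day 1, 2, 3, 4, 5 and Day 10 and end of study drug treatment". Table 14.2.1.1.11 repeats this under an ITT label: "The following time points will be shown: Day 1, Day 2, Day 3, Day 4, Day 5, Day 10", plus end of treatment.

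Four general SAP rules decide who enters the row:

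- Denominator (4.2.2): "Missing values will not be included in the denominator count when computing percentages".
- Missing data (4.2.4): "There is no imputation of missing values, unless specified otherwise". Section 6.2.2 specifies nothing for this endpoint. The same section does add: "Frequency of missing values will be tabulated for categorical variables".
- Extra post-dose samples (4.3.3): "Unscheduled samples will not be used in the descriptive statistics, but will be shown in listings".
- After a switch to open-label drug (4.3.6): "only data up to the switch are used in the analyses of these treatment groups".

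The schedules (Protocol Tables 2 and 3; SAP Appendix A) require a daily platelet count until daily PE ends. After that, counts fall 1, 8, 15 and 22 days after the last PE and at Day 30 of the post-PE period. Study Day 10 is counted from first dose (SAP 4.4.2). SAP 4.4 has visit windows in its heading but defines none for Day 10.

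**The concern.** Protocol 3.1.2 names platelet normalisation as the main reason for stopping daily PE. Stopping daily PE also ends daily counting. Whether a subject has a Day 10 count therefore depends on the outcome being tabulated and, if the drug works, on treatment. The subjects most likely to be absent are early responders, and more of them are expected on caplacizumab.

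A reader of an ITT-labelled table will take the row as the share of each randomised arm with a normal count on Day 10. Followed as written, it is the share among those not yet off PE, plus a few whose post-PE visit happens to fall on that day. Both the percentages and the contrast between arms are open to distortion. This is a named secondary endpoint in both documents, although it is not tested.

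**Working it through.** **The plan's own figure.** SAP 3.2 gives medians of 7 and 4.2 days, two-sided 5% and 80% power. The hazard ratio on the event-time scale is 4.2/7 = 0.6. Schoenfeld's formula gives 4(1.960 + 0.842)²/(ln 0.6)² ≈ 120.3, so 121 events. Exponential drop-out of 10% per 10 days over 45 days gives event probabilities of 0.897 and 0.940, mean 0.918; 132 × 0.918 ≈ 121. The stated 121 events and 132 subjects are reproduced, so exponential response at these medians is a fair base case.

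**Who has a Day 10 count.**

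- At nominal times: a last PE on Day 10 or later (still counted daily), on Day 9 (visit at +1 day) or on Day 2 (visit at +8 days). A last PE on Days 3–8 gives none.
- Using the ±1 day windows in SAP Appendix A in full: visits can fall 0 to 2 or 7 to 9 days after the last PE. A last PE on Days 4–7 still cannot give a Day 10 count.

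**Model.** The count on Day d is taken d − 1 days after first dose. Response time T is exponential with median m; the response is first seen on Day ceil(T) + 1, and the last PE is k days later. The protocol minimum is k = 2, and the endpoint allows up to k = 5. Responders are assumed to stay ≥150.

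- k = 2: a Day 10 count requires T > 5. Share with a count = 2^(−5/m). Row = P(5 < T ≤ 9)/P(T > 5) = 1 − 2^(−4/m).
- k = 5: a count requires T > 2. Share = 2^(−2/m). Row = 1 − 2^(−7/m).
- Reference A, cumulative response by Day 10 = 1 − 2^(−9/m): 77.4% vs 59.0%, difference 18.4 points.
- Reference B, the same with the planned 10% drop-outs counted as failures (× 0.9): 69.6% vs 53.1%, difference 16.5 points.

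Results, caplacizumab vs placebo:

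| Scenario | Have a count | Row shows | Difference (points) |
|---|---|---|---|
| k = 2 | 43.8% vs 61.0% | 48.3% vs 32.7% | 15.6 |
| k = 5 | 71.9% vs 82.0% | 68.5% vs 50.0% | 18.5 |
| Any count on Days 9–11, nominal visits, k = 2 | – | 56.1% vs 39.0% | 17.1 |
| Any count on Days 9–11, nominal visits, k = 5 | – | 73.3% vs 54.8% | 18.5 |
| Weibull shape 2, k = 2 | 37% vs 70% | 89.0% vs 54.6% | 34.4 |
| Phase II medians (3.0 vs 4.8 days), k = 2 | 31.5% vs 48.6% | 60.3% vs 43.9% | 16.4 |

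With 66 per arm, k = 2 leaves about 29 vs 40 subjects, or about 26 vs 36 after 10% drop-out (0.394 and 0.549 × 66).

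References for the last two rows:

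- Weibull: A is 95.9% vs 68.2% (27.7 points) and B is 86.3% vs 61.4% (24.9 points). Against B the row is about 3 points high on caplacizumab and 7 low on placebo.
- Phase II medians: A is 87.5% vs 72.7% (14.8 points).

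If Days 9–11 are accepted, visit windows fall favourably and k = 5, the row equals reference A. It is then 8 and 6 points above reference B.

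**Contrast with Day 5.** With k = 2 the earliest last PE is Day 4, so the visit one day later falls on Day 5. If that visit is counted, everyone still in the study has a Day 5 count. The problem in this model is specific to Day 10.

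**The case against.** The strongest reply is that this is one time point in one untested descriptive table. The number missing will be tabulated, so the unequal denominators will be visible. The Kaplan-Meier analysis of time to first count ≥150 is already planned on ITT (Table 14.2.1.1.9, Figure 14.2.1.1.5), and its curve already shows Day 10. Under exponential response the between-arm difference hardly moves: 15.6 to 18.5 points shown, against 18.4 or 16.5. The larger shift needs a Weibull shape with no source in the documents. The references are also cumulative response, whereas the row is status on the day. The SAP itself provides for counts falling back below 150 after response (Table 2, scenario 2), so true status may lie below 77% vs 59%.

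Most of this is correct, and it limits the consequence. The row cannot affect the primary conclusion or the type I error rate, and neither the size nor the direction of the error can be fixed in advance. It does not remove the fault. Printing the number missing shows a gap but leaves the percentage computed on a response-selected subset. Without a Day 10 window, it is also unclear whether a post-PE visit falling on that day counts at all.

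**Conclusion.** The point holds. Applied as written, the SAP's rules give a Day 10 row that carries an ITT label but describes a subset selected by response, with a smaller share of caplacizumab than placebo subjects in every scenario examined.

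At the planning medians with exponential response, nominal visits and no fall back below 150, the row is 29 vs 26 points below cumulative response if PE stops 2 days after response (77.4 − 48.3; 59.0 − 32.7). At 5 days it is 9 points below in each arm. Counting drop-outs as failures, the 5-day shortfall shrinks to 1 and 3 points. Under other curve shapes or visit mappings the row can be too high, and under the Weibull case it widens the treatment difference. The mechanism is certain; the size is scenario-dependent. The row should be corrected, but the confirmatory analyses are untouched.

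**What to change.** For Day 10, report by arm the Kaplan-Meier estimate with its confidence interval from the planned ITT analysis of time to first count ≥150 (SAP 6.1.2; Table 14.2.1.1.9), labelled *cumulative response by Day 10*. This largely avoids the gap. Daily PE is to continue for at least 2 days after 150 is reached, so the first such count normally falls while counting is daily. SAP 4.3.3 also lets this analysis use every sample: "Unscheduled measurements will be taken into account for derivation of time to event parameters and area under the curve (AUC").

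The cost is one printed estimate per arm from data already collected. There are two drawbacks to state in a footnote. It measures cumulative response, not status on the day. SAP Table 4 also censors early terminations, which would include deaths.

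If the status row is kept beside it, define a Day 10 window, state whether post-PE visits and unscheduled counts may fill it, show the number with a count out of the number randomised in each arm, and label it as restricted to subjects with a count. It should not be presented as an ITT comparison.

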Exacerbations and relapses will be documented as serious adverse events. Note that, exceptionally, daily PE may have been stopped before an initial platelet count $\geq 150 \times 10^9/L$ is reached, by investigator's decision. It is recognized that in this case the subject can still experience an exacerbation or relapse requiring re-initiation of daily PE if documented as described above.

- Treatment-emergent major thromboembolic event: e.g., myocardial infarction, cerebrovascular accident, pulmonary embolism or DVT, confirmed after adjudication (see below).

If a potential major thromboembolic event or TTP-related death occurs, the investigator will be requested to provide additional information for adjudication by a blinded independent committee. Only events that are confirmed after adjudication will be used for the analysis. More details are provided in CSP Section 3.4.3.6 and [Appendix B: Adjudication charter](#).

2. Proportion of subjects with a recurrence of TTP in the overall study period (including the FU period). A CMH test will be conducted with adjustment for GCS category (stratification factor used in randomization). For both treatment groups, only recurrences that have occurred prior to a potential switch to open-label caplacizumab will be evaluated for this analysis.
3. Proportion of subjects with refractory TTP, defined as absence of platelet count doubling after 4 days of standard treatment, and LDH $>$ ULN. A CMH test will be conducted with adjustment for GCS category (stratification factor used in randomization). Refractory TTP is derived as follows: (platelet count after 4 days of standard treatment / platelet count at start of standard treatment) $<$ 2 and LDH $>$ ULN after 4 days of standard treatment. Platelet count and LDH at Day 5 will be used for this analysis. Subjects who have reached platelet count response (primary endpoint) by Day 5 will not be considered as having a refractory TTP.

Subjects discontinued (lost to follow-up, withdrew consent, etc...) before day 5 will be excluded from the analysis.

CONFIDENTIAL

Missing values will be imputed using multiple imputation (Markov Chain Monte Carlo) by averaged simulated parameter values. The number of simulation iterations will be adapted to the proportion of missing values (0-10% missing values: 20 iterations, 10-20% missing values: 100 iterations) to keep the relative efficiency (RE) of multiple imputation under control (Rubin, 1987).

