6.2.2 Other secondary efficacy endpoints

Other secondary efficacy endpoints are defined in Section [3.3.2.2](#).

In general, all endpoints will be summarized using descriptive statistics such as number of observations, means, standard error, and proportions, as appropriate. All analyses will be run on the ITT population.

- Proportion of subjects with at least one treatment-emergent major thromboembolic event (e.g., myocardial infarction, cerebrovascular accident, pulmonary embolism or DVT), confirmed after adjudication, as well as the number of such events, during the overall treatment period (including extensions) (Caplacizumab, Placebo, OL Caplacizumab).
- Proportion of subjects with recurrences of TTP as well as the number of such events during study drug treatment (including extensions) and after study drug treatment (during FU) will be summarized by treatment group (Caplacizumab, Placebo, OL Caplacizumab).
- Proportion of subjects with treatment-emergent clinically significant TTP-related events, as well as the number of such events in the overall study period (including 4-week FU period) as defined in Section [3.3.2.2](#) will be summarized by treatment group (Caplacizumab, Placebo, OL Caplacizumab).
- Area under the curve (AUC) of platelet count until Day 5, truncated at $150 \times 10^9/\text{L}$ if platelet count is $150 \times 10^9/\text{L}$ or above, will be summarized by treatment group (Caplacizumab, Placebo). The AUC value will be calculated using the linear trapezoidal rule, i.e. $AUC_{t_i \text{ to } t_{i+1}} = 1/2 * (C_i + C_{i+1}) * (t_{i+1} - t_i)$ where C_i is the platelet count at time point t_i . Missing platelet counts will not be imputed separately as missing values can be bridged by using the trapezoid rule on neighboring (available) timepoints, thereby implicitly interpolating the missing timepoint. If the subject discontinued prior to Day 5, the subject will not be considered in this analysis. Descriptive statistics will include the 25%, 75% and 90% percentiles.
- Mortality rate (number and percentage) will be summarized by treatment group (Caplacizumab, Placebo, OL Caplacizumab) during DB treatment daily PE period (OL Caplacizumab not applicable), overall treatment period, FU period and overall study period.
- Organ damage markers:
 - Time to LDH $\leq 1 \times \text{ULN}$
 - Time to cTnI $\leq 1 \times \text{ULN}$
 - Time to serum creatinine $\leq 1 \times \text{ULN}$

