14.2.2 TTP

Table 14.2.1.2.1: EFF: TTP – Key secondary endpoint: Proportion of subjects with TTP-related death, a recurrence of TTP, or at least one treatment-emergent major thromboembolic event during the study drug treatment period

Frequency table of TTP-related death, a recurrence of TTP, or at least one treatment-emergent major thromboembolic event during the study drug treatment period and p-value of the Cochran-Mantel-Haenszel test with adjustment for GCS at randomization. Within the treatment emergent major thromboembolic events category the frequency tabulation of different preferred terms will be shown.

Population: ITT population.

Table 14.2.1.2.2: EFF: TTP – Key secondary endpoint: Proportion of subjects with a recurrence of TTP in the overall study period

Frequency table of recurrence of TTP in the overall study period and p-value of the Cochran-Mantel-Haenszel test with adjustment for GCS at randomization.

Population: ITT population.

Table 14.2.1.2.3: EFF: TTP – Key secondary endpoint: Proportion of subjects with refractory TTP

Frequency table of refractory TTP and p-value of the Cochran-Mantel-Haenszel test with adjustment for GCS at randomization.

Population: ITT population.

Table 14.2.1.2.4: EFF: TTP – Proportion of subjects with refractory TTP according to Scully et al. (2016)

Frequency table of refractory TTP according to Scully et al. (2016).

Population: ITT population.

Table 14.2.1.2.5: EFF: TTP – Proportion of subjects with treatment-emergent clinically significant TTP-related events

Number and percentage of subjects with and number of events of treatment-emergent clinically significant TTP-related events in the overall study period.

Population: ITT population.

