16.2 Efficacy

Listing 16.2.3.1: EFF: Platelet count

Listing per subject and time point of platelet count, including time to response and AUC.

Population: ITT population.

Listing 16.2.3.2: EFF: TTP

CONFIDENTIAL

Listing per subject of TTP related parameters (TTP related death, recurrence, TTP related AE).

Population: ITT population.

Listing 16.2.3.3: EFF: Organ damage marker levels

Listing per subject and time point of LDH, cTnI and serum creatinine values and abnormality flags and of the time to normalization parameters.

Population: ITT population.

Listing 16.2.3.4: EFF: Neurology

Listing per subject and time point of neurological symptoms, neurological assessment results and of SMMSE total score.

Population: ITT population.

Listing 16.2.3.5: EFF: Plasma Exchange

Listing per subject and time point of volume (absolute and normalized) of plasma exchange and of number of days of PE, total volume of PE and time to stop daily PE.

Population: ITT population.

Listing 16.2.3.6: EFF: Safety related parameters

Listing per subject of all safety related parameters.

Population: ITT population.

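### The SAP's derivation of consensus-defined refractory TTP leaves out the platelet limb below 50 x 10^9/L that its own definition contains (minor; one descriptive table)

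*SAP*

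**What the plan says.** The SAP has two refractory TTP endpoints. Key secondary endpoint 3 is based on failure of the platelet count to double, with LDH above ULN. The endpoint at issue here is the other one. It is listed in SAP 3.3.2.2, repeated in 6.2.2, and does not appear in the protocol's endpoint lists.

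**Definition.** In both SAP sections the platelet part has two alternatives, "lack of sustained platelet count increment or platelet counts" below 50 x 10^9/L. These are joined to LDH persistently above 1.5 x ULN, "despite 5 plasma exchanges and steroid treatment will be summarized by treatment group".

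**Derivation.** The same bullet of 6.2.2 then gives the programming rule. The platelet term requires the count on Day x to be below the "platelet count at Day x-1 for at least 1 value of x with x=2,...,5". The LDH term requires more than 1.5 x ULN from Day 1 to Day 5. Subjects in platelet response by Day 5 are set to not refractory. Missing values are multiply imputed, and subjects who discontinued before Day 5 are left out.

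**Output.** Table 14.2.1.2.4 is titled "Proportion of subjects with refractory TTP according to" the consensus paper, and its specification adds no further rule.

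**The concern.** The definition offers two ways to meet the platelet criterion, and the derivation implements one. A subject whose count never falls but stays very low, with LDH still raised, fits the words of the definition and is counted as not refractory. The table would then carry a published definition's name while reporting something narrower on that limb. A reader comparing the proportion with other work that uses the consensus definition would not know this from the table.

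**Working it through.** The plan states no figure for this endpoint, so there is nothing to reproduce. The check is logical.

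**Inputs.** From SAP 3.3.2.2 and 6.2.2:
- A = no sustained platelet rise
- B = platelets below 50 x 10^9/L
- C = LDH persistently above 1.5 x ULN

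The SAP renders A as at least one fall between consecutive days over Days 1 to 5. It gives no time point for B, so I take Day 5 as an assumption.

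**Rules compared.**
- SAP rule: A and C.
- Stated definition: (A or B) and C. The sentence could also be parsed as A or (B and C), so both were checked.

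**Results**, with LDH above 1.5 x ULN on all five days (counts x 10^9/L):

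| Days 1 to 5 | Any daily fall | Day 5 below 50 | SAP rule | Definition, either parsing |
|---|---|---|---|---|
| 10-15-20-25-30 | no | yes | not refractory | refractory |
| 12-12-12-12-12 | no | yes | not refractory | refractory |
| 10-20-30-40-49 | no | yes | not refractory | refractory |
| 10-15-12-20-30 | yes (15 to 12) | yes | refractory | refractory |
| 20-60-55-100-140 | yes (60 to 55) | no | refractory | refractory, with A as the SAP renders it |

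**Can any threshold act?** The SAP's platelet term uses only the order of consecutive counts. On a grid of 6^5 = 7,776 courses (daily values 10, 20, 30, 40, 60 or 100), adding 1000 to every count changed no classification. No absolute limit can operate.

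**Who is missed.** On that grid, adding B reclassifies 56 courses. These are exactly the non-falling courses that end below 50: five values in non-decreasing order from 10, 20, 30 and 40, which is C(8,5) = 56. The grid shows the logic and is not a prevalence estimate. The missed set is: no fall in any of the four daily intervals, Day 5 count below 50, and LDH above 1.5 x ULN on Days 1 to 5. A subject below 50 with a single dip is already caught.

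**Does anything restore the limb?** The exemption for platelet responders can only remove subjects. The imputation sentence supplies values, not thresholds. The table specification gives no rule, and SAP 12.1 does not mention the matter.

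**Why Day 5.** Protocol 3.2.1 requires one exchange before randomization, SAP 4.4.2 sets Day 1 as the first-dose day, and footnote a to protocol Table 2 places assessments before that day's exchange. With exchanges on schedule, the Day 5 sample follows 1 + 4 = 5 exchanges.

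**The case against.** The strongest reply is that little depends on this. SAP 6.2.2 introduces these endpoints with "In general, all endpoints will be summarized using descriptive statistics such as number of observations", so no test is attached and the endpoint is outside the fixed sequence. The rule is prespecified and leaves the analyst no choice. The missed set is narrow. Low counts are not hidden either: Table 14.2.1.1.13 gives platelet percentiles by time point and Table 14.2.1.3.7 gives LDH by time point. The listings supply "Listing per subject and time point of platelet count, including time to response and AUC" and "Listing per subject and time point of LDH, cTnI and serum creatinine values and abnormality flags". All of this stands and sets the severity. It does not make the table match its title, because the by-time-point tables are marginal summaries and cannot give the joint classification.

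A second reply is that a sponsor may operationalise a definition as it sees fit. It may, but here one of two alternatives disappears without comment while the consensus label stays.

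A reader might also infer that these subjects escape key secondary endpoint 3, perhaps below some cut-off in the Day 1 count. The documents do not support that. For endpoint 3 the SAP says "Platelet count and LDH at Day 5 will be used for this analysis", but the denominator is the count at the start of standard treatment, and one exchange precedes randomization. The imputation code lists Days 1 to 5, which makes Day 1 plausible, but no text settles it. For the course 10-15-20-25-30, a Day 1 denominator gives 30/10 = 3.0 and the subject is not flagged. A pre-exchange count of 20 gives 30/20 = 1.5 and the subject is flagged. No boundary can be claimed.

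**Conclusion.** The omission is real and holds under either parsing of the definition: as written, the limb below 50 x 10^9/L cannot classify any subject. The severity is minor. Primary and key secondary conclusions do not depend on it. Table 14.2.1.2.4 is the only output that names this definition; I assume that the other outputs by refractory status, which name none, use the key secondary one.

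The number of subjects affected, and any difference between arms, cannot be determined from the documents. The description of the missed set rests on reading the limb at Day 5.

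A reader might infer that adding the missing term would make the rule the full consensus definition. It would not. Any one-day dip would still count as lack of a sustained rise, so 20-60-55-100-140 with raised LDH would remain refractory, and steroid treatment is not a condition of the rule.

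**What to change.** In SAP 6.2.2, derive refractory TTP as [the existing fall condition OR Day 5 platelet count below 50 x 10^9/L] AND LDH above 1.5 x ULN from Day 1 to Day 5. Keep the exemption for subjects with platelet response by Day 5. Add one sentence stating that Day 5 is taken, by assumption, as the point after five exchanges.

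Describe Table 14.2.1.2.4 as a modified, operational version of the consensus definition, because the single-dip criterion and the absence of a steroid condition remain. If the term is not added, remove the consensus label from the table and text.

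The cost is one term in the derivation and program, one sentence, and a changed title. The new term is joined by OR, so it removes no subject already classed as refractory. Platelet count and LDH are already scheduled daily while daily exchange continues, so no new data are needed.
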